Hypothesis: We anticipate that the use of a venous closure device will decrease the time to hemostasis (TTH), time to ambulation (TTA) and time to discharge (TTD) compared to conventional methods of closure following venous access procedure.

III. Study Design & Methodology

This study will be a prospective, randomized study of patients who are undergoing one or more of the following procedures at ASLMC:

Large-Bore Procedures >13 F

- 1. WATCHMAN® device placement
- $2.\ Atrial\ fibrillation/flutter/SVT\ ablation\ using\ cryoballoon\ or\ laser\ balloon$
- 3. Leadless pacemaker
- 4. Pulmonary embolism thrombectomy (Inari FlowTriever system)
- 5. MitraClip transcatheter mitral valve repair

RANDOMIZATION:

Patients will be randomized into one of two venous closure groups after a clean stick has been achieved with no complications:

Large-bore (14F-25F) venous access group (1:1)
Perclose proglide smc
Figure 8 suture

Prior to enrollment a series of 110 randomization envelopes will be put together in a 1:1 to determine the closure strategy – Figure 8 suture or Perclose ProGlide SMC closure device for the large-bore procedures. Study investigators will draw an envelope to determine what group the subject will be randomized to only after sheath access has been achieved with no complications. Access should be ultrasound guided to guarantee a clean stick.

If randomization does not occur or if a complication not related to the Perclose ProGlide SMC closure device happens during the procedure the subject will be withdrawn from the study and considered a screen failure.

For both Perclose ProGlide SMC and figure 8 suture, supplemental manual compression may be used following device/suture placement if needed. If at any time the physician decides to use an alternate standard of care method as the primary method to achieve hemostasis other than that which the patient was randomized to, they may do so, and the patient will be considered a screen failure.

We will collect demographic data, past medical history, medication at the time of procedure, lab values at the time of procedure and post procedure, the need for blood transfusion, procedure details, and outcomes post procedure. *Study variables are listed in detail in the attached Excel file*.

Table 1: Schedule of Study Events:

Study Procedure	Screening	Day of Procedure	Follow-up (30 days post procedure)
Inclusion/exclusion	X		
Informed Consent		X	
Randomization to determine closure strategy		X	

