Data collection (medical history/baseline demographics, medications, lab values, procedure details, and outcomes post procedure)		X	X

IV. Eligibility

Inclusion criteria:

Large-bore (>13F) Venous Access Procedures Inclusion Criteria:

All patients 18 years and older who are undergoing any of the following: WATCHMAN® device placement, atrial fibrillation ablation using cryoballoon or laser balloon, leadless pacemaker, Pulmonary embolism thrombectomy (Inari FlowTriever system), MitraClip transcatheter mitral valve repair at Aurora St. Luke's Medical Center from date of IRB approval through December 2022. All arterial line access should be radial.

Exclusion criteria:

Large-bore (>13F) Venous Access Procedures Exclusion Criteria:

- Patients in whom introducer sheaths >25F were used in the vein during the catheterization procedure.
- Patients with small femoral arteries or veins (< 5 mm in diameter).
- Patients with access sites in vascular grafts.
- Patients with intra-procedural bleeding around access site. Patients who cannot receive radial arterial line access.
- Patients who have complications during the procedure not related to the Perclose ProGlide SMC closure device
- The physician determines that they must use an alternate method as the primary venous closure method other than that which the patient was randomized to
- Active systemic or cutaneous infection, or inflammation in vicinity of the groin
- Pre-existing immunodeficiency disorder or chronic use of high dose systemic steroids
- Known history of bleeding diathesis, coagulopathy, hypercoagulability or platelet count < 100,000 cells/mm3
- Severe co-existing morbidities with life expectancy less than 12 months

- Femoral arteriotomy or femoral venotomy in < 10 days, or with any known vascular complications or residual hematoma, or with use of an intravascular closure device w/in previous 30 days
- Planned femoral venous or arterial access within next 30 days
- Unable to routinely walk at least 20 ft. without assistance
- LMWH within 8 hours before or after procedure
- Pregnant and/or lactating women
- Extreme morbid obesity (BMI > 40 kg/m2) or underweight (BMI < 20 kg/m2)

V. Subject Enrollment

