An interim monitoring plan to perform periodic checks of the data after the first 25 subjects are enrolled and then again after 75 subjects are enrolled will be reviewed by the Biostatistician or study team to determine data integrity, accuracy, and consistency with the study objectives/hypotheses as well as preliminary analysis.

X. Statistical Considerations

A convenient sample size of approximately 55 subjects in each of the two randomized groups (Perclose ProGlide SMC and figure 8 suture) was determined to allow for parametric statistical methods. Following interim analysis: O'Brien-Fleming method was selected to adjust the p-value for interim analysis and final analysis. It was also used to calculate the required sample size at each stage of analysis in order to achieve 80% power in the outcome. Final sample size required was determined at 101 subjects. A 10% +/- should be added, to bring the total enrollment to 110 subjects.

XI. Outcomes

Primary outcomes: time to achieve hemostasis (TTH) and time to ambulate (TTA)

Secondary outcomes: time to discharge (TTD)/length of stay, post procedure major bleeding, mortality due to vascular complications, minor bleeding, access site hematoma, vascular thrombosis, vascular dissection, pseudoaneurysm, or AV fistula.

TTH: The elapsed time between "device" removal and first observed and confirmed venous hemostasis.

TTA: The elapsed time between removal of the final Perclose ProGlide SMC device (treatment arm) or removal of the final sheath (control arm), and the ability of subjects to stand and ambulate 20 feet without evidence of venous re-bleeding from the femoral access sites.

TTD/LOS: The elapsed time between removal of the final sheath, and the ability of subjects to be discharged. Length of hospital stay.

Major bleeding: Bleeding associated with ≥ 2 g/dl drop in hemoglobin level requiring transfusion, bleeding that occurs at a critical site, or bleeding contributing to death.

Minor Bleeding: Any bleeding that does not meet the criteria for major bleeding.

XII. Regulatory Requirements

Approval from the Aurora Health Care IRB will be obtained to perform this study, which includes approval of all associated informed consent forms. All protocol modifications and corresponding informed consent forms will be submitted for review and approval prior to implementing.

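### Two Section IV exclusions (access-site bleeding during the procedure, LMWH up to 8 hours after it) may be settled after randomization, and no analysis population keeps the affected patients in the comparison

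*Combined protocol and SAP*

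**What the plan says.** **Time of randomization.** Section III (Randomization) has the envelope drawn "only after sheath access has been achieved with no complications". This falls on the procedure day and before closure. No latest time for the draw is given.

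**Exclusions that can be settled later.** Section IV lists "Patients with intra-procedural bleeding around access site" and "LMWH within 8 hours before or after procedure". Two neighbouring bullets also refer to events at or after this stage: "Patients who have complications during the procedure not related to the Perclose ProGlide SMC closure device" and "The physician determines that they must use an alternate method as the primary venous closure method other than that which the patient was randomized to".

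**When eligibility is judged.** Table 1 marks inclusion/exclusion under Screening only and randomization under Day of Procedure.

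**What happens to the patient.** For a complication not related to the Perclose device, Section III says "the subject will be withdrawn from the study and considered a screen failure". A change of primary closure method also makes the patient a screen failure. Section III does not mention LMWH.

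**Analysis.** Sections IX and X name no intention-to-treat or other analysis set. Section XI makes time to hemostasis (TTH) and time to ambulation (TTA) primary. TTA requires walking without venous re-bleeding. Major and minor bleeding and access-site hematoma are secondary outcomes.

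**The concern.** An eligibility criterion protects the comparison only if it is judged before assignment. Once it is judged afterwards, by staff who know the arm, it becomes a rule for dropping randomized patients. The documents describe no blinding, and the investigators open the envelopes themselves.

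Access-site bleeding lies close to TTH, TTA and the bleeding outcomes, so removal on that ground is removal on something like the endpoint. The timing of LMWH after the procedure might depend on how well the closure is thought to have held. That is plausible, but the documents do not say it. If removal differs by arm, the estimate is biased and the type I error is not the stated one. Even if removal is balanced, it uses up the enrollment margin.

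**Working it through.** **1. Timing of each bullet against the draw**

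| Section IV bullet | Can it be settled before the draw? | Can it be settled after the draw? | Is removal written out? |
|---|---|---|---|
| Access-site bleeding during the procedure | Yes, if seen before the draw | Yes, for the rest of the procedure | Only if it counts as a complication under Section III |
| LMWH, window before the procedure | Yes | No | Ordinary exclusion |
| LMWH, window after the procedure | Only as planned use | Yes, for actual use | No; inferred from its place in the list |
| Complication not related to Perclose | Yes | Yes | Yes, Section III |
| Change from the randomized method | No | Always | Yes, Section III |

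The femoral re-access bullet in the same list is worded as planned access. The LMWH bullet has no such word.

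**2. The plan's own figure: 101 required, 110 enrolled (Section X)**

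- 101 × 1.10 = 111.1, rounded up to 112.
- 101 / 0.90 = 112.2, rounded up to 113.
- 110/101 − 1 = 8.9%.

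So 110 is consistent with adding roughly 10%. The 101 itself cannot be reproduced, because no effect size, SD or named outcome is given. The margin for all losses is 110 − 101 = 9 patients, or 9/110 = 8.2%.

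**3. Power if randomized patients are removed**

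The effect that gives 80% power with 101 patients at two-sided 0.048 (Section IX) is back-solved as

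d = (z₀.₉₇₆ + z₀.₈₀) × √(2/50.5) = 0.56 SD.

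| Patients analyzed | 110 | 101 | 95 | 90 | 80 |
|---|---|---|---|---|---|
| Power | 83% | 80% | 78% | 75% | 70% |

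**4. Bias and type I error**

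The removal rate, its split by arm and its correlation ρ with outcome are assumptions, because the documents give none of them. The simulation has no treatment effect, 55 v 55, a normal outcome, a t-test at 0.048 and 20,000 runs. In one arm, the k patients with the highest values of a marker S = ρX + √(1−ρ²)·e are removed, where X is the outcome and e is independent noise.

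| ρ | k removed | Bias (SD) | Type I error, one arm only | Type I error, k from each arm |
|---|---|---|---|---|
| 0.3 | 3 | −0.035 | 0.054 | 0.053 |
| 0.3 | 5 | −0.051 | 0.059 | 0.055 |
| 0.3 | 8 | −0.078 | 0.069 | 0.050 |
| 0.5 | 3 | −0.054 | 0.059 | 0.054 |
| 0.5 | 5 | −0.087 | 0.074 | 0.052 |
| 0.5 | 8 | −0.133 | 0.106 | 0.057 |
| 1.0 | 3 | −0.114 | 0.101 | 0.067 |
| 1.0 | 5 | −0.174 | 0.162 | 0.080 |
| 1.0 | 8 | −0.261 | 0.299 | 0.095 |

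The bias column is for one-arm removal. It scales with ρ, as it should: 0.5 × 0.174 = 0.087. When the same number is removed from each arm by the same rule, the difference in means is unbiased by symmetry. The error rate then stays near nominal at ρ of 0.3 or 0.5. It rises at ρ = 1 only because trimming the extremes makes the SD look too small.

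**The case against.** The strongest case on the other side has five parts.

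- **Much of this can be screened before the draw.** Bleeding at the stick already prevents randomization, and bleeding seen before the draw is a proper exclusion. With eligibility at Screening, the LMWH bullet can be read as planned use. This stands. A reader might infer that both criteria can be known only after randomization, and the text does not support that. What remains is bleeding after the draw and actual LMWH after the procedure, which the wording also covers.
- **Removal for LMWH is not stated.** This also stands. Withdrawal or screen failure is written out only for non-randomization, unrelated complications and change of method. But no sentence keeps the LMWH patient in, so the matter is left open.
- **The LMWH mechanism is conjecture.** It is. If LMWH were given sooner where closure held well, removal would take good performers and the bias would run the other way. The simulated direction should not be read as a prediction.
- **Bleeding before closure need not differ by arm.** This is fair, and balanced removal does little harm. Unblinded judgement of what counts as bleeding could still make it differ.
- **The neighbouring bullets are the clearer cases.** Change of method can only follow randomization, and the complication bullet is worded by reference to one arm's device. That is a reason for one remedy covering all four bullets. It does not justify leaving these two as they are.

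**Conclusion.** The point holds as a gap in wording and in the analysis plan. Two exclusions may be settled after assignment, and nothing in Sections IX and X keeps the affected patients in the comparison.

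The size cannot be computed from the documents. With 3 to 8 of 55 removed from one arm, type I error is about 0.05-0.07 at a correlation of 0.3, 0.06-0.11 at 0.5, and 0.10-0.30 at perfect correlation. The last range is a worst case: every removal is in one arm and strictly the slowest patients go. A reader might take it as the expected error rate, or infer that the device arm is favoured. The documents support neither, since they give no removal rate, no split by arm and no direction.

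The change is worth making because the gap is plain in the text and the repair costs little.

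**What to change.** 1. **Eligibility (Section IV).** State that every criterion is judged on what is known or planned before the envelope is opened. Keep the existing LMWH window, worded as given before or planned after. Keep the exclusion for access-site bleeding seen before the draw.
2. **Analysis set (Sections IX and X).** Add: *Every randomized patient is included in the primary analysis in the arm assigned, including any patient who after randomization has access-site bleeding, receives LMWH, has a complication or has a change of closure method.*
3. **Reporting.** Give the counts of these four events by arm, with a sensitivity analysis that excludes the patients concerned. Label it as no longer a fully randomized comparison.
4. **Consistency.** Reconcile Table 1, Section III and Section IV, so that screen failure applies only before the draw.
5. **Patients already removed, if any.** Restore them. Section VI names the electronic medical record as the data source, so their outcomes should be recoverable.

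**Cost.** A few sentences and no change to patient care. Outcome variance rises slightly, because patients with bleeding or a change of method stay in. Section XI starts the TTA clock differently in the two arms, so one line is needed on the start point for a patient whose closure method was changed. If all 110 are kept, power is about 83% for the effect that gives 80% at 101, before allowing for the extra variance.

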- Requires medical or surgical intervention to prevent life-threatening illness or injury or permanent impairment
- Fetal distress, fetal death, or congenital abnormality or birth defect

b. Reporting Requirements

All observed or volunteered adverse events occurring from the time of randomization to 30-days post randomization will be recorded in the subjects' case histories, regardless of the study group or suspected causal relationship. For all adverse events, sufficient information will be obtained in order to permit: 1) adequate determination of the seriousness, and 2) causal relationship of the adverse event. Adverse events or serious adverse events found to be a result of the treatment regimen will be followed until resolution of the adverse event.

Reportable adverse events include:

- Excessive Bleeding
- Hematoma
- Ischemia
- Infection
- Rash at access site

All adverse events and serious adverse events are to be reported to the Aurora Health Care Internal Review Board as outlined in the applicable policies.

c. Assessment of Relationship

The Principal Investigator is responsible for assessing the relationship of the adverse event or serious adverse event to the treatment.

IX. Data Analysis and Review

Continuous variables will be presented as means and standard deviation or median and interquartile ranges if normality is not assumed. Baseline demographic and medical data will be summarized and compared by standard descriptive statistical methods (ANOVA for continuous variables and Chi squared test for categorical variables or their non parametric equivalents). Comparisons will be made among groups based upon clinical factors using univariate regression to select potential independent predictors of outcomes (as defined in section III of the current document). Relevant potential independent predictors as determined by univariate analyses and expert clinical knowledge will then be included in multivariate regression models. Assumptions and goodness of fit will be assessed for each model. Statistical significance will be defined as a two tailed p value < 0.048 at final analysis. Further data analysis will be performed by clinical statistician (TBD).

A stratified analysis by French size or procedure type will be considered if there is evidence to suggest one is needed.

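### Section IX names no test of randomized arm on TTH or TTA, and the outcome modelling it describes leaves the primary result to an open choice among analyses

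*Combined protocol and SAP*

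**What the plan says.** The hypothesis in Section II is that "the use of a venous closure device will decrease the time to hemostasis (TTH), time to ambulation (TTA") and time to discharge, relative to conventional closure. Section XI makes TTH and TTA the primary outcomes and defines both, without a method of analysis.

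Section IX does the following:

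- It gives a rule for summaries: "Continuous variables will be presented as means and standard deviation or median and interquartile ranges if normality is not assumed". ANOVA, chi-squared and their non-parametric counterparts are named for baseline demographic and medical data only.
- It describes outcome modelling in two steps. First: "Comparisons will be made among groups based upon clinical factors using univariate regression to select potential independent predictors of outcomes". Then: "Relevant potential independent predictors as determined by univariate analyses and expert clinical knowledge will then be included in multivariate regression models". There is no entry threshold, covariate list or model type, and no statement that randomized arm is a term.
- It leaves stratification open: "A stratified analysis by French size or procedure type will be considered if there is evidence to suggest one is needed".
- It sets the final threshold: "Statistical significance will be defined as a two tailed p value < 0.048 at final analysis". The sentence does not say which comparison is tested.
- It leaves further analysis to a statistician still to be named.

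Section X mentions parametric methods and 80% power for an outcome that it does not name.

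**The concern.** A randomized trial needs one stated comparison of the arms per primary outcome, fixed before the outcomes are seen, so that a reader can check the reported p-value against the plan. Section XIII(c) requires analysis as specified in the protocol, and for the primary comparison there is nothing specific to check against.

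Two things are at stake. First, an unadjusted comparison, a screened model, a stratified analysis and a rank test are all compatible with the text, and they can disagree about significance. Second, the written rule chooses terms by their univariate results. Applied literally, it could leave out arm if arm failed the screen. It could also admit a variable measured after randomization: Section III collects "lab values at the time of procedure and post procedure, the need for blood transfusion, procedure details, and outcomes post procedure", and the visible text does not exclude such variables from screening. If arm affects a variable of that kind, adjusting for it removes part of the effect the trial is meant to estimate.

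**Working it through.** **Inputs from the documents:** 101 subjects required, 1:1 allocation, 80% power (Section X); two-sided 0.048 (Section IX). The documents give no effect size, SD, covariate strength or number of candidates, so those are assumed below.

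**The plan's own figure.** N = 101 cannot be reproduced forwards. Solved backwards with the two-sample normal formula, d = (z₀.₉₇₆ + z₀.₈₀)·√(2/50.5) = (1.977 + 0.842) × 0.199 = 0.561. With the t distribution at 51/50, d = 0.567: the noncentrality is 0.567·√(51·50/101) = 2.849 on 99 df, and power is 80.0%. This d is used throughout.

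**Step 1: each analysis alone, and the choice between two.** Simulated with 8,000 runs per cell (Monte Carlo SE about 0.24 points for type I error and 0.45 for power). Assumed: procedure type and French size carry all the prognosis (R² in the first column), there are 15 noise candidates, screening is at p < 0.10, and arm is always in the model.

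| R² | Type I: unadjusted | Type I: screened | Type I: smaller of the two p-values | Power: unadjusted | Power: screened | Opposite sides of 0.048 under a true effect |
|---|---|---|---|---|---|---|
| 0% | 4.7% | 4.8% | 5.9% | 79.9% | 76.4% | 6.7% |
| 10% | 4.7% | 4.4% | 6.4% | 79.7% | 79.8% | 10.4% |
| 20% | 4.6% | 4.7% | 7.1% | 80.9% | 84.9% | 11.9% |
| 30% | 4.7% | 4.8% | 7.4% | 80.4% | 89.4% | 14.1% |

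Other simulations with different covariate structures gave 5.7–8.0% for the smaller p-value, and 4.4–5.4% for single analyses. The smallest of four analyses, including a rank test, rejected in about 9.0%. Choosing only between a t-test and a rank test gave 5.7–6.9%.

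Not all of the disagreement in the last column is arbitrary. At R² = 30% the screened model gains 89.4 − 80.4 = 9.0 points of power. So it alone is significant in (14.1 + 9.0)/2 = 11.6% of trials, and the unadjusted test alone in (14.1 − 9.0)/2 = 2.6%. At R² = 0 the direction reverses: (6.7 − 3.5)/2 = 1.6% against (6.7 + 3.5)/2 = 5.1%.

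**Step 2: arm subjected to the screen.** If arm must itself pass p < 0.10, power is 76.2/78.3/81.8/83.9% at R² = 0/10/20/30%. Against the screened column above, the loss is 0.2/1.5/3.1/5.5 points.

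**Step 3: a post-randomization variable enters (conditional).** Simulated with 20,000 runs; the within-arm correlation of the variable with the outcome is 0.3 or 0.5. If 10% of the arm effect runs through the variable, power is 74.2% or 82.2%. If 25%, it is 56.6% or 67.0%, and the mean arm coefficient is about 0.43 (0.567 × 0.75 = 0.425). If 50%, it is 26.1% or 33.8%.

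**Step 4: power of a fixed covariate list.** With three extra parameters the noncentrality is about 2.849·√(1 − 3/99)/√(1 − R²) on 96 df. Power is then 78.8/82.9/87.0/91.0% at R² = 0/10/20/30%. If the covariates are not prognostic, the loss against the unadjusted test is 80.0 − 78.8 = 1.2 points (80 − 78 = about 2 by simulation). Against screening, the answer depends on where the prognosis lies:

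| Assumed source of prognosis | Fixed (procedure, French size) | Screened | Difference |
|---|---|---|---|
| Procedure and French size, R² 20% | 86.4% | 84.9% | +1.5 |
| Two other candidates, R² 20% | 78.5% | 84.9% | −6.4 |
| Two other candidates, R² 30% | 78.2% | 89.2% | −11.0 |
| 20% elsewhere, 10% in procedure and French size | 81.8% | 89.0% | −7.2 |
| 20% elsewhere, 5 other candidates | 79.1% | 86.6% | −7.5 |

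A further run with the prognosis elsewhere gave 80% against 85.5%, a loss of 5.5 points.

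**The case against.** The strongest reply is that the arm comparison is present but loosely drafted. The protocol uses the word groups for the randomized arms in Sections III and X, and a univariate regression on arm is the two-sample t-test. A two-tailed threshold, an O'Brien-Fleming adjustment and a power target all presuppose a comparison of arms. That reading is possible. Even so, the sentence ties the comparison to clinical factors and to selecting predictors, and it fixes no scale, effect measure or model to which 0.048 applies.

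Second, Section IX refers to Section III, which cites an attached file of study variables that is not visible here. That file may list candidate covariates, so it cannot be said that none are specified anywhere. It is described as a list of variables, not as a statement of the primary test.

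Third, Section III's list is a data-collection list, and Section IX speaks of clinical factors. A reader might infer that the plan intends to adjust for transfusion or post-procedure laboratory values. The documents do not say so; they only fail to rule it out. Step 3 is therefore conditional.

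Fourth, a reader might infer that screening inflates the error rate, or that fixed covariates always give more power. Neither is supported. The screened model alone stays near nominal, and the fixed list loses power when the strong predictors are not on it.

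**Conclusion.** The point holds. Section IX does not state which comparison of the arms is primary for TTH or TTA, and its written modelling rule does not guarantee that arm is in the model or that covariates precede randomization. The size is moderate and rests entirely on assumed inputs: about 6–8% false positives if the better of an unadjusted and a screened result were used, against a nominal 4.8%. With a true effect, the two analyses fall on opposite sides of the threshold in roughly 7–14% of trials, partly because their power differs.

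Two stronger conclusions are tempting. One is that the most favourable result will be reported; nothing in the plan says so, and the defect is that a reader could not check. The other is that this text was written with outcomes by arm in view. Section X's wording about what followed the interim analysis raises the question but does not settle it.

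Whether 0.048 suits the planned looks, how error is shared between TTH and TTA, and which patients are analysed are separate matters and are not decided here.

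**What to change.** In Section IX, replace covariate screening for the primary analysis with one prespecified comparison per primary outcome.

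1. Always include randomized arm, apply the final threshold to the arm effect, and report that effect with a confidence interval.
2. State one outcome scale. If times are expected to be right-skewed, log time keeps a parametric method and yields a ratio of times. On assumed lognormal times with log-SD 0.5 or 1.0, power was 80.5% or 80.8% on the log scale, against 75.8% or 61.0% on the raw scale. State how zero times are handled.
3. Adjust only for a short list known before the envelope is drawn. Procedure type and sheath French size, already named in Section IX, are candidates, because the envelope is drawn "only after sheath access has been achieved with no complications". Add any other strong pre-randomization predictor, chosen without outcome data. A prespecified unadjusted comparison would also be acceptable.
4. Label screened, stratified and rank analyses as sensitivity or exploratory.
5. Date the amendment and state whether outcomes by arm had been seen when it was written.

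The cost is a short amendment; no new visits are needed, and procedure details are already collected. About 1–2 power points are lost against an unadjusted test if the covariates are not prognostic. Under the assumed inputs, roughly 5–11 points are lost against a screened model if the strong predictors are left off, so the list deserves care.

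### TTH and TTA are both primary at a single 0.048 threshold, and the plan does not say whether one or both must succeed

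*Combined protocol and SAP*

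**What the plan says.** - Section XI (Outcomes) names two primary outcomes and does not rank them: "Primary outcomes: time to achieve hemostasis (TTH) and time to ambulate (TTA"). Time to discharge (TTD) is listed there as secondary.
- Section IX (Data Analysis and Review) sets one criterion: "Statistical significance will be defined as a two tailed p value < 0.048 at final analysis".
- Section X (Statistical Considerations) gives the source of that figure: "Following interim analysis: O'Brien-Fleming method was selected to adjust the p-value for interim analysis and final analysis". This is an adjustment for repeated looks. Section X says nothing about two outcomes.
- Section X also says the sample size was calculated "in order to achieve 80% power in the outcome". The outcome is singular and is not named. The resulting size is 101 subjects, raised to 110 for enrollment.
- Section II (Objectives and Specific Aim) predicts that the device will "decrease the time to hemostasis (TTH), time to ambulation (TTA) and time to discharge (TTD").
- Section IX provides for data checks after 25 and 75 subjects, "reviewed by the Biostatistician or study team to determine data integrity, accuracy, and consistency with the study objectives/hypotheses", together with a preliminary analysis.

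No section states an either-or-both rule, a testing order, a division of alpha between the outcomes, or any other correction for having two.

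**The concern.** O'Brien-Fleming boundaries control error over repeated looks at one hypothesis. They give no protection across two hypotheses tested at the same look. If TTH and TTA are each compared with 0.048, each test keeps its own 4.8% error. What the trial may conclude from the pair is undefined.

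The practical problem is a split result. If TTH reaches p < 0.048 and TTA does not, or the reverse, the text does not say whether the trial met its primary objective. Reporting that as success means applying an either-counts rule, which inflates the error for the pair. Requiring both controls the error, but then the power that matters is the power for joint success, and the plan does not give it. A rule settled after someone has seen which outcome looks better would not repair this. The study team may see interim data, so the timing of the rule matters.

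**Working it through.** **The plan's own figures.** The 101 subjects cannot be reproduced, because the documents give no effect size, no standard deviation and no named outcome. Solved backwards with 50.5 per arm, two-sided 0.048 and 80% power, it implies a standardized difference of (1.977 + 0.842) × √(2/50.5) = 0.56. The 0.048 is reproduced by an O'Brien-Fleming design with one interim look at half the information (simulated final level 0.0481). It therefore carries no allowance for a second outcome. Formal looks at 25 and 75 of 110 would give about 0.045. That is a separate matter, and 0.048 is taken as given here.

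**Inputs.** From the documents: two primary outcomes (Section XI), two-sided 0.048 at the final analysis (Section IX), 80% power and 101 subjects (Section X). Assumed: one test per outcome with approximately normal statistics, and a correlation ρ between them. The documents give no correlation, so a range is shown.

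**Formulas, final test only.** The critical values are c = 1.977 (two-sided 0.048) and c′ = 2.257 (two-sided 0.024).

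- Either counts, no effect on either, false finding in either direction: 1 − P(|Z₁| ≤ c, |Z₂| ≤ c). At ρ = 0 this is 1 − 0.952² = 0.0937.
- The same, counting only findings that favor the device: 1 − P(Z₁ ≤ c, Z₂ ≤ c), with positive values favoring the device. At ρ = 0 this is 1 − 0.976² = 0.0474.
- Holm, no effect on either: 1 − P(|Z₁| ≤ c′, |Z₂| ≤ c′). At ρ = 0 this is also 1 − 0.976² = 0.0474, but it counts both directions.
- Both required, each outcome with 80% power: P(both significant). At ρ = 0 this is 0.80² = 0.64.

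| ρ | Either counts, any direction | Either counts, favoring device | Holm, any direction | Joint power, both required |
|---|---|---|---|---|
| 0 | 9.4% | 4.7% | 4.7% | 64% |
| 0.5 | 8.7% | 4.4% | 4.5% | 69% |
| 0.7 | 8.0% | 4.0% | 4.1% | 71% |
| 0.8 | 7.5% | 3.8% | 3.9% | 73% |
| 0.9 | 6.8% | 3.4% | 3.5% | 75% |

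For a single test the comparable errors are 4.8% in any direction and 2.4% favoring the device. The either-counts figure falls below 7% only when ρ exceeds about 0.87, and reaches 4.8% only at ρ = 1. If the device truly affects one outcome, the false-finding chance on the other is 4.8%. Adding one O'Brien-Fleming look at half the information raises the either-counts total slightly, to 9.8% at ρ = 0 and 7.8% at ρ = 0.8. If both are required, the false-claim rate is at most 4.8%. If the second outcome has 90% power instead of 80%, joint power is 72% to 79% (ρ from 0 to 0.9).

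**Power under Holm at 101 subjects.** With 80% power at 0.048, the mean of the test statistic is 1.977 + 0.842 = 2.819. If only one outcome has an effect, its power against 0.024 is Φ(2.819 − 2.257) = Φ(0.562) = 0.71; the second Holm step adds almost nothing (0.713 to 0.715). If both outcomes have 80%, each has 0.775 at ρ = 0 and 0.751 at ρ = 0.9.

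**Size for 80% joint power, equal effects.** At ρ = 0 each outcome needs power √0.80 = 0.894, so z = 1.250. Then 101 × (1.977 + 1.250)² / 2.819² = 132.4, or 134 with equal arms. At ρ = 0.9 the result is 113.2, or 114.

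**The case against.** The strongest reply is that the plan means both outcomes. Section XI joins them with the word and, and the hypothesis in Section II predicts a decrease in all of TTH, TTA and TTD. Under that reading no error is inflated. This is a natural reading and it limits the concern, but it does not settle it. The word in Section XI joins items in a list, and the hypothesis includes a secondary outcome, so it cannot be the success rule for the primary ones. Requiring both would also leave the 80% power unexplained.

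A reader might infer that the trial runs a 7-9% risk of falsely declaring the device better. The documents do not support that. They never say that one outcome is enough, and the figure counts false findings in both directions. Under the either-counts rule the risk in the device's favor is about half as large.

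A reader might also infer that the outcome to emphasize has been, or will be, picked from interim results. The documents do not show this. Section X says only that the O'Brien-Fleming method was chosen following an interim analysis, and Section IX says who may review interim data. These facts are a reason to fix the rule independently of those data. They are not evidence of misuse.

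Two further objections stand in part. Section IX names no primary test, describes regression modeling and leaves further analysis to a statistician still to be named, so the percentages are indicative. And this is a single-center study of a device that Section I describes as already approved for femoral vein closure, with no regulatory claim in view, which limits the weight of the point.

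**Conclusion.** The concern holds as an unstated success rule for two primary outcomes. Its consequence depends on the rule eventually applied. Under either-counts, the pair has roughly 1.4 to 2 times the error of one test (6.8/4.8 to 9.4/4.8), if the device affects neither outcome. Under both-required, error is controlled and the shortfall is in power: 64-75% for joint success if 80% applies to each outcome. These sizes rest on one approximately normal test per outcome, an assumed correlation of 0 to 0.9, and the final test alone. Results for TTH and TTA remain interpretable one at a time; the trial-level claim is what is undefined. This should be corrected before the final analysis, but it does not invalidate the design.

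**What to change.** Before the final analysis, and without using interim data, state one rule in Sections IX and XI.

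- **Option 1, Holm.** Compare the smaller of the two p-values with 0.024; if it is significant, compare the other with 0.048. The cost is the loss of per-outcome power shown above: from 80% to about 71% if only one outcome has an effect, or to about 75-78% for each if both have 80%.
- **Option 2, both required.** Both outcomes must reach p < 0.048. Section X then says whether its 80% is per-outcome or joint power. The cost is that the power for success becomes 64-75% if each outcome has 80%.

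Holm suits the trial if a benefit on one outcome alone is worth claiming; otherwise the second option fits. That choice belongs to the investigators.

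Under either option, add a sentence on interim looks, because a rule for the final threshold does not cover them. Either no efficacy claim on TTH or TTA is made at an interim look, or the same split is applied to the interim boundary. TTD and the other secondary outcomes stay supportive.

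The change is one or two sentences in Sections IX and XI, and one in Section X if power is restated. No extra patients are needed. Only a decision to hold 80% joint power would raise the required size, from 101 to about 114-134 (correlation 0.9 to 0, equal effects).
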